APPENDIX C MEDICATIONS THAT PROLONG QTc

Generic name	Brand name] [Generic name	Brand name
Amiodarone	Cordarone®] [Haloperidol	Haldol®
Arsenic trioxide	Trisenox®] [Ibutilide	Corvert®
Astemizole	Hismanal®] [Mesoridazine	Serentil®
Azithromycin	Zithromax®] [Methadone	Dolophine®
Bepridil	Vascor®] [Moxifloxacin	Avelox®
Chloroquine	Aralen®] [Pentamidine	Pentam®
Chlorpromazine	Thorazine®] [Pimozide	Orap®
Clarithromycin	Biaxin®] [Probucol	Lorelco®
Disopyramide	Norpace®] [Procainamide	Procan®
Dofetilide	Tikosyn®] [Quinidine	Quinaglute®
Domperidone	Motilium®] [Sotalol	Betapace®
Droperidol	Inapsine®] [Sparfloxacin	Zagam®
Erythromycin	Erythrocin®] [Terfenadine	Seldane®
Flecainide	Tambocor®] [Thioridazine	Mellaril®
Halofantrine	Halfan®] [Vandetanib	Caprelsa®

For the most current list of medications, please refer to the following website: www.torsades.org

APPENDIX D ORAL IRINOTECAN ADMINISTRATION GUIDELINES

- The hospital pharmacist will provide you with 5 doses of irinotecan, each in an oral syringe. Because irinotecan has an unpleasant taste, it is usually mixed with a small amount of juice **IMMEDIATELY BEFORE** giving the medicine to your child.
- The best juice to use is CranGrape Juice, although CranApple or cranberry juice is fine as well.
- **DO NOT** mix the irinotecan in orange juice, apple juice, milk or soda.
- Use a disposable cup to mix the irinotecan with juice. The amount of juice used is up to you. The more juice used, the more the flavor of the irinotecan will be masked. However, it is critical that your child drink ALL of the juice mixed with irinotecan. Most parents start by mixing the irinotecan in about one teaspoon (5 ml) of juice. Discard the cup when empty after the irinotecan + juice has been taken.
- Irinotecan should be mixed with juice only on the day the dose is given. The other doses should be stored in a **REFRIGERATOR**. Irinotecan will last for 21 days at a time, provided it has not been mixed with juice.
- Use of nausea medicines (Zofran, Kytril, or Anzemet) may be helpful, and these medicines are best given about 30-60 minutes before the irinotecan. Please discuss this with your doctor.

If you are unable to take the medicine, or vomits within 30 minutes of taking the medicine, please call your doctor for further instructions.

APPENDIX E PATIENT INSTRUCTIONS FOR TREATING DIARRHEA

Dear Patient or Parent:

You are receiving irinotecan. This drug can cause severe diarrhea. Before your FIRST chemotherapy treatment please be sure to:

1. BUY IMODIUM A-D. Make sure you have this medication at home before your first chemotherapy treatment. Imodium A-D is also called LOPERAMIDE and comes in 2 mg caplets and in liquid form at a concentration of 0.2mg/ml.

2. AFTER your chemotherapy has started, at the FIRST SIGN of diarrhea be sure to START taking Imodium A-D. DO NOT DELAY starting Immodium A-D if you notice your stools to be more loose, soft, or watery than usual. Do not skip doses. Give Immodium A-D as follows:
> 43 kg (95 pounds) and more: 4 teaspoonfuls or 2 caplets after first loose stool followed by 2 teaspoonfuls or 1 caplet every two hours as needed.

• 20-43 kg (44-94 pounds): take 2 teaspoonfuls or 1 caplet after the first loose stool followed by one teaspoonful or one-half caplet every 2 hours as needed.

3. STOP taking IMODIUM when you HAVE NOT had any bowel movements for 12 hours.

4. Call your doctor if you still have diarrhea after taking Imodium for 24 hours, or if there is fever or vomiting, or if you have any questions.

5. Your diarrhea can also get a little better if you take the following steps IN ADDITION TO taking Imodium A-D:

- Drink plenty of water or Gatorade

- Drink broth or clear soup to replace salt

- Stay away from milk, dairy products, alcohol, hot or cold beverages, coffee, tea and drinks with Caffeine

6. Do not take medicines such as Miralax, Mylanta, Maalox, Senokot, or Colace

7. Eat foods that are easy to tolerate such as bananas, rice, apple sauce, chicken (white meat), white toast, and canned fruits

8. Please fill out the Irinotecan Administration Diary below during this treatment and give to your nurse or physician.

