5.3.3 Concomitant Medications

Eribulin has been associated with prolonged QTc, so medications that prolong QTc should be avoided when possible. A list of medications that prolong QTc is provided in Appendix C.

5.3.4 Supportive Care

Appropriate antibiotics, blood products, antiemetics, fluids, and general supportive case are to be used as necessary.

5.3.5 Prophylaxis for Irinotecan-Associated Diarrhea

Cefixime or an available equivalent antibiotic will be used to reduce irinotecan-associated diarrhea as previously mentioned [44, 45]. Antibiotic treatment should start at least two days prior to the start of irinotecan. This antibiotic therapy should continue until 3 days after the last dose of irinotecan.

5.3.6 Concomitant Medications for Diarrhea and Abdominal Cramping

Patients and their families will be instructed to contact their physician if diarrhea occurs. Any patient who develops diarrhea or abdominal cramping within the first 4 hours after oral administration of irinotecan should receive atropine intravenously at a dose of 0.01 mg/kg (maximum 0.4 mg). This so-called "early onset diarrhea" is often presaged by cholinergic manifestations such as diaphoresis and abdominal cramping. Because patients are treated with irinotecan over multiple days, it may be difficult to distinguish immediate from delayed diarrhea. Patients with presumed immediate diarrhea who do not improve with atropine, or patients who develop diarrhea more than 4 hours after receiving irinotecan, should be given treatment with oral loperamide for late onset diarrhea as outlined below.

All patients will receive a copy of instructions for the use of loperamide if/when diarrhea occurs (Appendix D). Each family will be provided with this antidiarrheal medicine with instructions to start at the first episode of poorly formed or loose stools, or at the earliest onset of bowel movements more frequent than normally expected for the patient.

Loperamide (1 mg/5 ml or 1 caplet = 2 mg) dosing guidelines for diarrhea: Weight \geq 43 kg (\geq 95 pounds): Take 4 teaspoonfuls or 2 caplets after the first loose stool, followed by two teaspoonfuls or one caplet every two hours as needed. Weight 20 kg to 43 kg (\leq 94 pounds): Take 2 teaspoonfuls or 1 caplet after the first loose stool, followed by one teaspoonful or one-half caplet every 2 hours as needed.

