Because patients will be receiving prolonged exposure to antibiotics (i.e., cefixime), patients having significant diarrhea should have stool samples evaluated for *C difficile* toxin, as this is a potentially treatable cause of diarrhea. If patients have fever with diarrhea, or bloody diarrhea, evaluation of stools for bacterial culture should also be performed.

If there is failure of loperamide to control diarrhea after 24 hours of use, patients may receive octreotide (SandostatinTM) at the dose of 10 micrograms/kg/dose subcutaneously every 12 hours x 3 days.

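### Appendix E item 4 gives the patient a later call trigger than Section 5.3.6 and omits diarrhea or cramping within 4 hours of an irinotecan dose

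*Combined protocol and SAP*

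**What the plan says.** Section 5.3.6 ties contact to the occurrence of diarrhea, with no waiting period: "Patients and their families will be instructed to contact their physician if diarrhea occurs". It then separates two forms.

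- **Early form:** "Any patient who develops diarrhea or abdominal cramping within the first 4 hours after oral administration of irinotecan should receive atropine intravenously", at 0.01 mg/kg up to 0.4 mg. The section adds that this form "is often presaged by cholinergic manifestations such as diaphoresis and abdominal cramping".
- **Late form:** oral loperamide, for diarrhea that starts more than 4 hours after a dose or for presumed early diarrhea that atropine does not relieve.

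The section also has families start loperamide at the first loose stool, whatever the timing, and concedes that "it may be difficult to distinguish immediate from delayed diarrhea". The 24-hour mark comes at the end, as a rescue step: "If there is failure of loperamide to control diarrhea after 24 hours of use, patients may receive octreotide".

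Appendix E is the sheet the patient holds. Item 2 says to start Imodium at the first sign of diarrhea, with doses by weight. Item 4 is its only instruction on calling: "Call your doctor if you still have diarrhea after taking Imodium for 24 hours, or if there is fever or vomiting", or with any questions.

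Section 5.2 allows inpatient or outpatient treatment. Appendix D shows that the family is handed five syringes of irinotecan to keep in a refrigerator.

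**The concern.** The protocol body and the patient's sheet give different occasions for calling, and the sheet's is the later one. Loperamide can be started at home without help. Intravenous atropine cannot: someone at the site has to hear of the symptoms first. A patient who does exactly what Appendix E says takes Imodium and, unless there is fever, vomiting or a question, has no written reason to call for 24 hours. By then the moment for treating symptoms that began within 4 hours of a dose has gone. Cramping without loose stool triggers nothing on the sheet, although under Section 5.3.6 cramping alone in that window qualifies for atropine. What is at stake is the care of the individual patient.

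**Working it through.** No arithmetic underlies the main point; it is a comparison of texts.

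| Situation | Section 5.3.6 | Appendix E |
|---|---|---|
| First loose stool: loperamide | Start at once | Start at once (item 2); agrees |
| First loose stool: contact | Contact the physician | No prompt |
| Diarrhea within 4 hours of a dose | Intravenous atropine | Not distinguished |
| Cramping within 4 hours of a dose | Intravenous atropine | Not mentioned |
| Sweating as a warning sign | Named | Not mentioned |
| Diarrhea after 24 hours of loperamide | Octreotide may be given | Call (item 4) |

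The 24-hour call on the sheet therefore lines up with the octreotide step, not with first contact.

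**Do other patient-held pages fill the gap?**
- Appendix B deals with drug interactions.
- Appendix D asks for a call if a dose cannot be taken or is vomited within 30 minutes.
- The Appendix F diary records stools and when Imodium was started. The Section 10 footnote has it returned before the next cycle, too late to act as a prompt.
- None of them mentions atropine or early-onset diarrhea.

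These three pages were not written to give diarrhea call instructions. The check shows only that nothing elsewhere makes up for item 4.

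**Which doses are exposed?** In cycle 1, Sections 5.2 and 9.1.1.1 require blood sampling up to 5 hours after eribulin on day 1, and irinotecan follows eribulin by at least 15 minutes. With irinotecan at 0.25 hours, the 4-hour window closes at 0.25 + 4 = 4.25 hours, inside the sampling period. It stays inside as long as irinotecan is given within 5 - 4 = 1 hour of eribulin. No upper limit on that delay is stated, so this is an assumption, but the first dose is probably observed. Sampling is confined to cycle 1, and days 2-5 carry no required visit in the Section 5.2 delivery map beyond an optional blood sample. That leaves 4 of the 5 doses in cycle 1, and the doses of later cycles, without this cover.

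**How often?** The irinotecan table in Section 7.2.2 puts cholinergic symptoms, including hyperperistalsis with cramping and early diarrhea, in the band above 20% of patients, and lists immediate diarrhea again in the band below 20%. The table is not specific to the oral five-day schedule, and the share of doses taken at home is not given. No count of affected patients can be derived.

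**The case against.** The strongest reply is that Section 5.3.6 never assigns the contact instruction to Appendix E. It says families will be instructed, without naming a vehicle, and separately says they receive a sheet on using loperamide. Appendix E does that job: same first action, essentially the same weight bands and doses. The contact instruction may be given by staff or in the consent form, whose pages are not in the public file. All of this stands, and it rules out two stronger readings. A reader might infer that Appendix E fails to carry out Section 5.3.6 as a whole, or that patients will not be told to call at onset; the documents support neither. What remains is that the sheet at home gives a later trigger than the one staff are meant to convey.

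The invitation to call with questions is not an onset trigger, since a patient with clear instructions to take Imodium has no evident question. That early and late diarrhea are hard to tell apart does not excuse the omission either; it is a reason for the site to hear at onset and make the judgment.

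Two further inferences should be resisted.

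- **That the stakes follow from diarrhea being the dose-limiting toxicity of protracted irinotecan.** Section 2.3 attributes irinotecan diarrhea to mucosal injury by SN-38 and a secretory mechanism. Atropine in Section 5.3.6 is for the early cholinergic form. The documents do not say that the early form is the dose-limiting one.
- **That missed atropine would distort DLT counts,** because Section 5.5.2 excludes grade 3 diarrhea when appropriate supportive care, atropine included, was not given. No rate is available, nothing shows that untreated early symptoms lead to grade 3 diarrhea beyond 3 days, and grade 3 diarrhea of 3 days or less is excluded anyway.

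**Conclusion.** The point holds as a mismatch between a handout and the protocol body. It is a cheap patient-safety improvement, not a flaw in the design or analysis. Item 4 has a later call trigger than Section 5.3.6 and omits the one situation in which 5.3.6 calls for a treatment that cannot be given at home. The conclusion assumes that some doses are taken at home, which the plan permits but does not quantify, and that patients consult the sheet when symptoms start. It does not depend on whether staff also give the onset instruction: if they do, the two sources conflict. No effect on DLT assessment or the RP2D is claimed.

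Two slips nearby are clerical only. Section 5.3.6 points to Appendix D for loperamide instructions that are in Appendix E. It also says "Each family will be provided with this antidiarrheal medicine", while Appendix E item 1 tells the patient to buy it.

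**What to change.** Reword Appendix E item 4 along these lines:

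- Start Imodium at the first sign of diarrhea, and call your doctor when diarrhea occurs.
- Call right away if diarrhea or abdominal cramping starts within 4 hours of an irinotecan dose. Sweating may be an early warning sign.
- Call again if diarrhea continues after 24 hours of Imodium, or for fever, vomiting or questions.

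Sweating should appear as a warning sign, not as a trigger of its own, because Section 5.3.6 gives atropine for diarrhea or cramping. In the same revision, correct the Section 5.3.6 pointer to Appendix E and state one source for loperamide.

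The cost is one handout revision, which needs IRB approval under Section 12.3, two clerical edits, and more patient calls. There is no new data collection and no change to the DLT definition.

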APPENDIX F ORAL IRINOTECAN ADMINISTRATION DIARY

 Patient Name
 Course #_____

Day of course	Date	Time Irinotecan Given	Time Cefixime Given	Number of stools	Consistency (F=Formed L=Loose W=watery)	Mark when Imodium A-D was started
-1*						
0*						
1						
2						
3						
4						
5						
6						
7						
8						
9						
10						
11						
12						
13						
14						
15						
16						
17						
18						
19						
20						
21						

*Course 1 only

APPENDIX G PHARMACOKINETIC STUDY FORM

Study Date	 Patient ID	 DOB:	
*Gender	 *Race	 *Ethnicity	
BSA (m²)	 Height (cm or ft:in)	 Weight (lb or kg)	

*This information is requested on a voluntary basis to account/explore potential differences in pharmacokinetics

Eribulin:	Dose (mg/m2)
Start time Notes:	: Stop time:
_	
Irinotecan	: Dose (mg/m2)

Administration time:	
Notes:	

Each sample for the PK study is to be 7 ml of whole blood collected into a sodium heparinized collection tube. All times listed in the table below are relative to the start of the eribulin IV dose. Each tube must be labeled with the patient's study ID number, time and date the sample was drawn. Data should be recorded on this Pharmacokinetic Study Form.

Blood sample collection		
	Date of Collection	Time of Collection
Pre dose		
15 min after end of infusion		
1 hr after end of infusion		
1.5 hr after end of infusion		
2 hr after end of infusion		
4 hr after end of infusion		
5 hr after end of infusion		
24-96 hr after end of infusion (optional)		
Pre dose (day 8)		

Processing and shipping instructions for plasma samples

A sample processing and handling kit containing all the consumables, labels, and storage containers will be provided for a set of 5 patients. Upon receipt keep all materials including the shipping box. Refer to shipping instructions below.

Whole blood samples will be collected from the central line or a peripheral IV provided a flush of at least 10 ml of normal saline has been administered. At each time point, \sim 7 ml of venous blood will be withdrawn into two 4-mL sodium heparin collection tubes.

PK sample processing:

- 1) Immediately upon collection place blood sample (heparinized) tubes in wet ice and note the collection time on the sample collection timesheet.
- 2) Transfer blood sample into 4 clear siliconized microcentrifuge tubes. Centrifuge the blood samples for 2 min at 7200 g to separate plasma (top layer) from red blood cells.
- 3) Transfer plasma into two amber siliconized tubes, with a plastic transfer pipet. Discard red cells. Cap the tubes.
- 4) Complete information on the labels and affix onto each tube.
- 5) Store samples on dry ice and transfer into the provided storage container (81 or 100 slot box) before storing in the -80°C freezer.

Shipping instructions:

